5.1.5 Prophylactic Medicines and Supportive Care

All prescription and non-prescription medications including pharmacologic doses of vitamins, herbal medicines, or other non-traditional medicines, taken from thirty days prior to the first dose of ACY-1215 through the End of Study Visit must be recorded in the CRF.

Patients will be permitted to receive appropriate supportive care measures as deemed necessary by the treating physician including but not limited to the items outlined below:

- **Diarrhea:** Diarrhea should be treated promptly with appropriate supportive care, including loperamide. Loperamide should not be taken prophylactically. Patients should be instructed to begin taking loperamide at the first sign of: 1) poorly formed or loose stool, 2) occurrence of more bowel movements than usual in one day or 3) unusually high volume of stool. Loperamide should be taken in the following manner: 4 mg at first onset of diarrhea, then 2 mg after each unformed stool. The daily dose of loperamide should not exceed 16 mg/day. Loperamide should be deferred if blood or mucus is present in the stool or if diarrhea is accompanied by fever. In this setting, appropriate diagnostic microbiologic specimens should be obtained to exclude an infectious etiology. Patients should also be advised to drink liberal quantities of clear fluids.
- **Nausea/vomiting:** ACY-1215 is not emetogenic. Standard institutional guidelines for anti-emetics will be used. Nausea and vomiting should be treated aggressively, with agents such as prochlorperazine, metoclopramide, 5-HT-3 inhibitors, or benzodiazepines. Patients should be strongly encouraged to maintain liberal oral fluid intake during therapy. Patients who experience indigestion or gastroesophageal reflux symptoms may be treated with Proton Pump Inhibitors (PPIs) as well as H2 blockers as clinically indicated. High dose steroids (> 10 mg QD of prednisone equivalent) are to be avoided as an anti-emetic therapy.
- **Growth Factors:** Patients who have pre-existing chronic anemia prior to receiving ACY-1215 may continue to receive erythropoietin or darbepoietin. After initiating treatment, anemia may be managed with growth factors according to the ASCO guidelines: 2006 Update of Recommendations for the Use of White Blood Cell Growth Factors: An Evidence-Based Clinical Practice Guideline
<http://www.jco.org/cgi/content/full/24/19/3187>.

Post cycle 1, colony stimulating growth factors (e.g., filgrastim, peg-filgrastim, and sargramostim) may be used in patients who experience hematological toxicity per

American Society of Clinical Oncology (ASCO) guidelines. Furthermore, patients who are not receiving such prophylaxis who experience febrile neutropenia (a DLT if occurring in Cycle 1) may receive treatment with colony stimulating factors at the Investigator's discretion. Neulasta should not be administered given that there is no data for co-administration of ACY-1215 with neulasta.

- **Thrombocytopenia:** Transfusion of platelets may be used if clinically indicated. Dose modification for thrombocytopenia is allowed in a manner consistent with the guidelines for dose modification (Section 6).

5.1.6 Excluded Medications and Substances

The following medications and supportive therapies and procedures are prohibited during the study:

- Any investigational agent other than ACY-1215, including agents that are commercially available for indications other than lymphoma that are under investigation for the treatment of lymphoma.
- Any anti-neoplastic treatment with activity against lymphoma other than study drug.

5.2 Duration of Therapy

Treatment may continue until one of the following criteria applies:

- Disease progression
- Unacceptable adverse event(s), DLTs
- Withdrawal of consent
- General or specific changes in the patient's condition render the patient unacceptable for further treatment in the judgment of the investigator
- An event that in the judgment of the treating physician warrants discontinuation of therapy
- Termination of the study

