5.1.4 Dose-Limiting Toxicity

A dose limiting toxicity (DLT) is defined as any toxicity not specifically included in section 5.1.4 that occurs within cycle 1. DLT is also defined as any toxicity, occurring up to 7 days after completion of cycle 1 that results in a delay of initiating cycle 2. For patients who discontinue study drug administration after Cycle 1, DLT will be defined as any toxicity not specifically included in section 5.1.4 that occurs within 30 days of the last dose of drug on study, in cycle 1 that is not related to disease progression.

DLTs include:

Hematologic dose-limiting toxicity will be defined as either Grade 4 neutropenia that does not resolve to \leq Grade 2 within \leq 7 days, any Grade 4 thrombocytopenia, or any Grade 5 hematologic toxicity. At least three patients in each cohort must be evaluable for hematologic toxicity.

Non-hematologic dose-limiting toxicity will be defined as any Grade 3, 4 or 5 non-hematologic toxicity, with the exception of:

- Grade 3 nausea or Grade 3 vomiting that occurs in the setting of inadequate compliance with supportive care measures specified in Section 5.1.7 and lasts for less than 48 hours.
- Grade 3 diarrhea that occurs in the setting of inadequate compliance with supportive care measures specified in Section 5.1.7 and lasts for less than 48 hours.
- Grade 3 dehydration that occurs in the setting of inadequate compliance with supportive care measures specified in Section 5.1.7 and lasts for less than 48 hours.
- Grade 3 acidosis or alkalosis that responds to medical intervention by returning to \leq Grade 2 within 48 hours.
- Isolated (i.e. no other abnormalities) Grade 3 elevation of liver function tests (LFTs) without associated clinical symptoms, lasting for \leq 5 days in duration.
- Isolated (i.e. no other abnormalities) Grade 3 elevation of amylase without associated clinical symptoms, lasting \leq 5 days
- Grade 3 hypocalcemia, hypokalemia, hypomagnesemia, hyponatremia, or hypophosphatemia that responds to medical intervention.

- Grade 3 hypercholesterolemia.
- Grade 3 hypertriglyceridemia
- Grade 2 Alopecia
- Grade 3 Constipation
- Grade 3 Fatigue

Management and dose modifications associated with the above adverse events are outlined in Section 6.3.

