5.4 Criteria for Removal from Study

Patients will be removed from treatment when any of the criteria listed in Section 5.2 applies. The reason for study removal and the date the patient was removed must be documented in the patient's chart and the CRF.

Subjects/patients may withdraw at any time or be dropped from the study at the discretion of the investigator should any untoward effects occur. In addition, a subject/patient may be withdrawn by the investigator if he/she violates the study plan or for administrative and/or other safety reasons. The investigator or study coordinator will notify the appropriate parties within 2 business days when a subject has been discontinued/ withdrawn due to an adverse event (Section 7). When a subject discontinues/withdraws prior to study completion, all applicable activities scheduled for the end of study visit should be performed at the time of discontinuation. Any adverse events present at the time of discontinuation/withdrawal will be followed until resolution.

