6.3.1 ACY-1215 Dose Modifications

In general, if study drug has been held and the toxicity does not resolve, as defined above, then drug must be discontinued. Note: Dose reductions should not be performed for alopecia or for nausea or vomiting that was not treated with aggressive anti-emetic support. Dose modifications are described in detail in the table below.

Table 2: Dose Modifications for ACY1215

Dose Modifications for ACY1215	
CTCAE Grade or Abnormal Value	1) ACY1215
Thrombocytopenia	
Grade 1 ($75 \times 10^9/L - < LLN$) Grade 2 ($50 - < 75 \times 10^9/L$)	Maintain dose level 2) Maintain dose level
Grade 3 or 4 thrombocytopenia: OR Thrombocytopenia that requires platelet transfusion or recurrent Grade 3 or 4 thrombocytopenia	Hold subsequent doses of therapy until thrombocytopenia returns to \leq Grade 2 or baseline and continue at full dose Hold subsequent doses of therapy until thrombocytopenia returns to \leq Grade 2 or baseline and permanently reduce dose of ACY1215 to 75% of dose. If the same toxicity recurs despite dose reduction, reduce by an additional 25%.
Neutropenia (ANC)	
3) Grade 1 ($1.5 \times 10^9/L - < LLN$) 4) Grade 2 ($1.0 - < 1.5 \times 10^9/L$)	5) Maintain dose level 6) Maintain dose level
7) Grade 3 and 4 neutropenia:	8) Hold subsequent doses of therapy until specific cytopenia returns to \leq Grade 1 or baseline and continue at full dose
9) Febrile Neutropenia	
Febrile ($\geq 38.5^\circ C$) Grade 4 neutropenia or recurrent Grade 3 or 4 neutropenia:	10) Hold subsequent doses of therapy until neutropenia returns to \leq Grade 1 or baseline and permanently reduce dose of ACY1215 to 75% of dose. If the same toxicity recurs despite dose reduction, reduce by an additional 25%.
11) All Other Non-Hematologic Drug Toxicities (not mentioned in previous tables)	
Grade 1 or 2:	12) Maintain dose level
Grade 3	Hold treatment with ACY1215 until toxicity returns to \leq Grade 1 or baseline, then restart therapy at full dose. If Grade 3 toxicity recurs, reduce dose of by 25%. This is a permanent dose reduction.
Grade 4	Grade 4 toxicity: Hold treatment with ACY1215 until toxicity returns to \leq Grade 1 or baseline, and then restart therapy at 25% dose reduction. This is a permanent dose reduction

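### Sections 5.2 and 5.4 require removal from treatment after a DLT, while Table 2 holds and resumes drug after several of the same cycle 1 events

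*Combined protocol and SAP*

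**What the plan says.** Section 5.2 opens with "Treatment may continue until one of the following criteria applies", and one item in the list that follows is "Unacceptable adverse event(s), DLTs". Other items in that list are left to the judgment of the investigator or treating physician; this one is not. Section 5.4 then states: "Patients will be removed from treatment when any of the criteria listed in Section 5.2 applies".

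Section 5.1.4 defines DLTs, essentially within cycle 1. Hematologic DLTs include Grade 4 neutropenia that has not improved to Grade 2 or better within 7 days, and "any Grade 4 thrombocytopenia, or any Grade 5 hematologic toxicity". For the rest, "Non-hematologic dose-limiting toxicity will be defined as any Grade 3, 4 or 5 non-hematologic toxicity", subject to a list of exceptions. Section 5.1.5 also calls febrile neutropenia in cycle 1 a DLT. Directly after its list of exceptions, Section 5.1.4 says: "Management and dose modifications associated with the above adverse events are outlined in Section 6.3".

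Table 2 in Section 6.3.1 gives hold-and-resume instructions by grade. For Grade 3 or 4 thrombocytopenia the instruction begins "Hold subsequent doses of therapy until thrombocytopenia returns to" and ends with full-dose continuation, or with a reduction if a transfusion is needed or the event recurs. For the most severe non-fatal non-hematologic events it begins "Grade 4 toxicity: Hold treatment with ACY1215 until toxicity returns to" and ends with a restart at a 25% reduction. In Section 6, treatment ends when an interruption exceeds 14 days (6.1) or when toxicity does not resolve (6.3.1). DLT status is not a trigger there.

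The synopsis list of reasons to stop keeps unacceptable adverse events but does not mention DLTs.

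**The concern.** Two parts of the protocol give a site opposite instructions for the same serious toxicity. One ends treatment; the other pauses it and starts it again. Two sites could each follow the text literally, manage the same event in opposite ways, and each be open to a finding of protocol deviation.

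The first stake is patient safety. The second is what the trial reports. Time to treatment failure is listed among the Phase II primary objectives (Section 1.2.1), and Section 12.7 tabulates discontinuations due to adverse events. Both depend on whether a patient with a DLT is taken off drug. The exposure summaries in Section 12.5 depend on it too. The DLT definition is not limited to Phase Ib, so the conflict can reach Phase II.

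**Working it through.** No sample size, power or event count is involved, so the check sets the rules side by side. Inputs: the DLT definitions (5.1.4, 5.1.5), the removal rule (5.2 with 5.4), and the dose-modification rules (6.1, 6.3.1 with Table 2).

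| Event in cycle 1 | Source of DLT status | 5.2 with 5.4 | Table 2, once recovered |
|---|---|---|---|
| Grade 4 thrombocytopenia | 5.1.4 | Remove from treatment | Full dose; reduced if transfusion needed or recurrent |
| Grade 4 neutropenia, not at Grade 2 or better within 7 days | 5.1.4 | Remove | Full dose; reduced if recurrent |
| Febrile Grade 4 neutropenia | 5.1.5 | Remove | Reduced dose |
| Grade 3 non-hematologic, outside the exceptions | 5.1.4 | Remove | Full dose; reduced if recurrent |
| Grade 4 non-hematologic | 5.1.4 | Remove | 25% reduction |

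All five rows conflict. Next, the edges of the conflict:

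1. *Grade 5 events.* These are DLTs but have no row in Table 2. No conflict.
2. *Toxicity that does not resolve, or a hold longer than 14 days.* Section 6 ends treatment, as do 5.2 and 5.4. No conflict.
3. *Events after the DLT window, and the exceptions listed in 5.1.4.* These are not DLTs, so 5.2 does not reach them by that term. No conflict.
4. *What remains.* Cycle 1 DLTs of the five kinds that recover within the 14-day limit.

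Is there an exemption anywhere? Neither Section 6 nor Table 2 excludes cycle 1, Phase Ib or DLTs. Section 5.1.5 allows dose modification for thrombocytopenia under Section 6 without excluding DLTs. One kind of DLT in 5.1.4 is a toxicity that delays the start of cycle 2, which presupposes that cycle 2 can follow.

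Finally, which results depend on the answer?

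- *Phase Ib expansion decisions:* these use the number of patients with a DLT (12.1.1). A DLT counts whether or not the patient stays on drug, so the rule itself is untouched.
- *Time to treatment failure:* the protocol does not define it. If, as assumed here, stopping drug for toxicity counts as failure, removal is an event in cycle 1 and re-treatment is not.
- *Discontinuations due to adverse events, and exposure:* both change directly with the rule followed.
- *Response:* the first on-treatment scan falls within 7 days before cycle 3 (10.1), so a patient removed in cycle 1 stops drug before it. A re-treated Phase II patient can also drop out of the response analysis, because missing more than 10% of planned dose leads to censoring for response and replacement (4.5, 6.1). If this is counted over one 28-day cycle, 2 missed days are 2/28 = 7.1% and 3 missed days are 3/28 = 10.7%, so a hold of 3 days is enough. The protocol does not state the denominator.

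**The case against.** The best defence is that the texts can be harmonised. DLT is a cycle 1 concept and Table 2 a general table for all cycles, so 5.2 with 5.4 could be the specific rule and Table 2 the rule for everything else. The sentence in 5.1.4 that points to Section 6.3 fits this reading: it follows the list of exceptions and may cover only those events, which are not DLTs. That point stands. The cross-reference is ambiguous, and it cannot be used to say that 5.1.4 sends DLTs to Table 2.

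The harmonised reading is nevertheless nowhere written. Table 2 has explicit Grade 4 rows with no cycle limit, and no sentence says which section prevails. The permissive opening of 5.2 does not help either, because 5.4 turns each criterion into a mandatory removal.

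The synopsis is weak evidence for either side. It is a shorter list that keeps unacceptable adverse events and physician-judged events, so it needs aligning but is not a separate contradiction.

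A reader might also infer that a patient removed for a cycle 1 DLT becomes un-evaluable, with losses to response and PFS. The documents do not support that. Section 12.3.2.1 concerns patients who discontinue the study before response evaluation, whereas the sentence in 5.4 removes them from treatment. Follow-up continues about every 3 months until progression or new therapy (5.1.3), response is assessed at least every 6 months after therapy stops (10.3), and one day of therapy plus a re-evaluation makes a patient evaluable (10.3.1).

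**Conclusion.** The conflict is real and holds in a limited form. For cycle 1 DLTs of the five kinds in the table that recover within 14 days, the protocol requires removal in one place and resumption in another, and gives no order of precedence. It affects patient safety, the count of discontinuations due to adverse events, exposure summaries and, on the assumption stated above, time to treatment failure.

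It would go too far to say that every cycle 1 DLT is affected, since fatal and non-resolving events are not. Nor can a number of affected Phase II patients be given. The documents contain no DLT rate for this schedule in lymphoma. The earlier monotherapy experience reported no DLTs in 15 patients, but in myeloma and on an intermittent schedule, so any count would rest on an assumed rate. An effect on response is possible but partial, because the missed-dose rule may exclude re-treated patients as well.

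No view is taken on which clinical rule is right.

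**What to change.** State in one place what happens to a patient after a DLT, separately for Phase Ib and Phase II if the rules differ, and bring the other texts into line with it:

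- Sections 5.2 and 5.4: say whether a DLT always ends treatment.
- Section 6.1 and Table 2: say whether the hold-and-resume rows apply to cycle 1 DLTs.
- Section 5.1.4: say which events the reference to Section 6.3 covers.
- Synopsis: align the list of stopping reasons.

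The investigators make the clinical choice. The cost is protocol wording, with the amendment review and IRB approval that Section 11.5 requires. Sample size, visits and analyses do not change.

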5.3 Patient Adherence to Protocol Schedule

All patients are required to adhere to the protocol-specified visit schedule. If the patient misses the D1 visit of any cycle, attempts should be made to reschedule the visit within the following 2 days. Failure to attend scheduled study visits may result in discontinuation from the study.

Patients will be required to maintain a log of the precise time at which they had last ingested food prior to taking ACY-1215, the time at which they took study drug, and the time at which they next ingested food.

5.4 Criteria for Removal from Study

Patients will be removed from treatment when any of the criteria listed in Section 5.2 applies. The reason for study removal and the date the patient was removed must be documented in the patient's chart and the CRF.

Subjects/patients may withdraw at any time or be dropped from the study at the discretion of the investigator should any untoward effects occur. In addition, a subject/patient may be withdrawn by the investigator if he/she violates the study plan or for administrative and/or other safety reasons. The investigator or study coordinator will notify the appropriate parties within 2 business days when a subject has been discontinued/ withdrawn due to an adverse event (Section 7). When a subject discontinues/withdraws prior to study completion, all applicable activities scheduled for the end of study visit should be performed at the time of discontinuation. Any adverse events present at the time of discontinuation/withdrawal will be followed until resolution.

5.5 Duration of Follow Up

Patients will have an end of study visit 4 weeks +/- 7 days after their last dose of drug to evaluate safety. Patients will be further followed every three months after the 4-week safety evaluation for one year, or until they develop a POD or begin a new treatment for their disease, for evaluation of delayed toxicity. Patients removed from study for unacceptable adverse events will be followed until resolution or stabilization of the adverse event.

6. DOSING DELAYS/DOSE MODIFICATIONS

6.1 Dose Delays

- Study drugs will be held until adverse event returns to \leq Grade 2.
- If interruption lasts for more than 14 days, study treatment will be discontinued.
- In patients who miss $>10\%$ of planned dose in the Phase II, but not the Phase Ib, data will be censored for response, but not for toxicity, and patients will be replaced for adequate response assessment.

6.2 Resuming Administration of Study Drug

For toxicities that can be treated or prevented, such as nausea, vomiting, diarrhea and neutropenia, mucositis, treatment may be resumed at the previous dose once supportive measures have been instituted and toxicity recovers to Grade 2 or less.

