5.1.3 Required Blood Parameters and Other Investigations Prior to Each Treatment

Before the start of each treatment cycle, patients should be reassessed and the following criteria must be fulfilled:

- Karnofsky Score \geq 70 or ECOG Performance Status \leq 2

- ANC > 1000/dL
- Platelet count \geq 50,000
- Serum creatinine concentration $\leq 2.0 \times$ ULN or \leq baseline, or creatinine clearance >30 mL/min
- AST (SGOT) and ALT (SGPT) $\leq 3.0 \times$ ULN or $\leq 3.0 \times$ ULN in presence of demonstrable liver metastases
- Bilirubin concentration $\leq 2.0 \times$ ULN
- Recovery of any drug-related non-hematological toxicity to Grade 1 or less, unless otherwise indicated

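### Sections 6.1 and 6.2 let drug resume at Grade 2 or less, while Table 2 requires Grade 1 or baseline after severe neutropenia or non-hematologic toxicity, and the restart doses also differ

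*Combined protocol and SAP*

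**What the plan says.** Four places in the protocol govern when held drug may restart.

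- **Section 6.1, Dose Delays**, covers every adverse event: "Study drugs will be held until adverse event returns to" Grade 2 or less. It also ends treatment when an interruption exceeds 14 days.
- **Section 6.2, Resuming Administration of Study Drug**, covers toxicities that can be treated or prevented, "such as nausea, vomiting, diarrhea and neutropenia, mucositis". For these, "treatment may be resumed at the previous dose once supportive measures have been instituted and toxicity recovers to Grade 2 or less".
- **Section 6.3.1, Table 2**, sets its own levels. For Grade 3 and 4 neutropenia it says "Hold subsequent doses of therapy until specific cytopenia returns to" Grade 1 or less, or baseline. For Grade 3 and for Grade 4 non-hematologic toxicity it says "Hold treatment with ACY1215 until toxicity returns to" the same level. Both thrombocytopenia hold rows use Grade 2 or less, or baseline. The text above the table requires discontinuation if a held toxicity does not resolve, and refers back to a definition given earlier.
- **Section 5.1.3, Required Blood Parameters** (the second section with that number), lists among its conditions for starting a cycle: "Recovery of any drug-related non-hematological toxicity to Grade 1 or less, unless otherwise indicated".

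Two further rules depend on how long drug is held. Sections 4.5 and 6.1 censor for response, and replace, any patient who misses more than 10% of planned dose; 6.1 limits this to Phase II. The treatment plan common to both phases sets a cycle at 28 or 56 doses and does not allow missed doses to be made up.

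**The concern.** Section 6.2 permits what Table 2 forbids, for the same patient on the same day. Two sites could each follow a section of the protocol and treat identical patients differently, one re-dosing and the other continuing to hold. That is a safety matter first.

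It also reaches the analysis. Days on hold count as missed doses, and missed doses decide whether a Phase II patient is counted for response or replaced. Response rate is the Phase II primary endpoint and is judged on small counts: 2 responses among 22 patients to continue, and 8 in the final criterion. A rule that moves even a few patients in or out of the evaluable set should not depend on which page a site reads.

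**Working it through.** The plan gives no figure to reproduce here, so the check sets the rules side by side and then follows hold length into the rules that use it.

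**1. Recovery level and restart dose, by event**

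| Event causing the hold | 6.1 | 6.2 | Table 2 level | Table 2 restart dose | Agreement |
|---|---|---|---|---|---|
| Grade 3-4 thrombocytopenia | Grade 2 | not named | Grade 2 or baseline | full | level agrees |
| Thrombocytopenia, transfused or recurrent Grade 3-4 | Grade 2 | not named | Grade 2 or baseline | 75% | level agrees |
| Grade 3-4 neutropenia | Grade 2 | Grade 2, previous dose | Grade 1 or baseline | full | level conflicts |
| Febrile Grade 4, or recurrent Grade 3-4, neutropenia | Grade 2 | Grade 2, previous dose | Grade 1 or baseline | 75% | level and dose conflict |
| Grade 3 non-hematologic | Grade 2 | Grade 2, previous dose, if treatable | Grade 1 or baseline | full; 25% lower if it recurs | level conflicts; dose conflicts on recurrence |
| Grade 4 non-hematologic | Grade 2 | Grade 2, previous dose, if treatable | Grade 1 or baseline | 25% lower | level and dose conflict |

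Each grade in the table means that grade or less. Section 6.3.1 exempts nausea or vomiting that was not treated with aggressive anti-emetic support from dose reduction. For those events only the recovery level is in conflict.

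**2. One patient traced through**

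Take a patient with a normal baseline neutrophil count whose Grade 4 neutropenia, without fever, has improved to Table 2's Grade 2 band, 1.0 to below 1.5 × 10⁹/L. Section 6.2 names neutropenia and allows restart. Table 2 keeps the patient on hold until Grade 1. If the patient's baseline already lay in that band, which Section 3.1 allows (entry from 1.0 × 10⁹/L), both rules would release the patient.

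**3. Does the text say which rule governs?**

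Preferring the specific rule to the general one does not settle it, because 6.2 is itself specific and names a toxicity that has its own row in Table 2. Section 6.3.1 does not settle it either. Its discontinuation sentence points back to a definition of resolution, which reads most naturally as 6.1 and 6.2, while the table beneath it uses a different level in most rows.

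**4. Effect on the 14-day rule**

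Let *h* be the days held until Grade 2 and *g* the further days until Grade 1 or baseline. The hold lasts *h* under 6.1 and 6.2, and *h* + *g* under Table 2. The outcome differs when *h* ≤ 14 < *h* + *g*: the patient continues under the first reading and is discontinued under the second.

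**5. Effect on the more-than-10% rule (Phase II)**

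The smallest number of missed doses that passes the limit is floor(0.10 × planned doses) + 1. The protocol does not state the counting period, so each row is an assumption.

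| Assumed period | Once daily | Twice daily | Full held days |
|---|---|---|---|
| 1 cycle | 3 of 28 (10.7%) | 6 of 56 (10.7%) | 3 |
| 2 cycles | 6 of 56 (10.7%) | 12 of 112 (10.7%) | 6 |
| 6 cycles | 17 of 168 (10.1%) | 34 of 336 (10.1%) | 17 |

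With *L* the number of days in the last column, the two readings classify a patient differently only when *h* < *L* ≤ *h* + *g*. On a per-cycle count with *h* = 2, the first reading gives 2/28 = 7.1% and the patient stays evaluable. One extra day (*g* = 1) gives 3/28 = 10.7% and the patient is censored and replaced. On a six-cycle count, a single hold would pass the 14-day limit before reaching 17 days, so only repeated holds could matter. The documents give no values for *g*, so the number of patients affected cannot be derived.

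**The case against.** The strongest reply is that 6.2 is permissive: it says treatment may resume. A site that always waits for Table 2's level breaches nothing in 6.2, so the rules could be read as a minimum in 6.1 and 6.2 with a further condition in Table 2. That reading is workable, but the protocol does not state it. A site that restarts at Grade 2 under 6.2 follows one section and breaches another.

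Several limits do stand:

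- The conflict does not run through all of Table 2; the thrombocytopenia rows agree with 6.1.
- The baseline alternative removes it for patients who entered at Grade 2.
- Section 5.1.3 is only secondary support. It is a cycle-start check, covers drug-related non-hematologic toxicity only, and gives way where another rule is indicated.

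A reader might go further in three ways that the documents do not support.

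- One might infer that a Grade 2 event lasting more than 14 days ends treatment under Table 2. It does not. Table 2 maintains the dose for Grade 2 neutropenia and for Grade 1 or 2 non-hematologic toxicity, so such an event starts no hold. The 14-day limit sits in 6.1 and counts the whole interruption, including days at Grade 3 or 4.
- One might take 10.7% as the size of the effect on response evaluability. It only shows where the missed-dose limit falls under an assumed counting period, and that limit applies whichever recovery level is used.
- One might say the conflict decides who counts in the response rate. It can affect that, in Phase II, for patients whose extra hold days carry them over a limit. No more can be shown.

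**Conclusion.** Wrong as written. This is an internal contradiction, not a design choice. Sections 6.1 and 6.2 and Table 2 set different recovery levels for restarting drug after Grade 3-4 neutropenia, febrile or recurrent neutropenia, and Grade 3-4 non-hematologic toxicity. Section 6.2 and Table 2 also set different restart doses after Grade 4 non-hematologic toxicity and after febrile or recurrent neutropenia. The patients concerned are those whose Grade 3-4 event has improved to Grade 2 but remains above their baseline.

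The case for correction rests on the dosing contradiction alone. The consequence for the primary endpoint is real in direction but unquantified: it depends on the time from Grade 2 to Grade 1 and on the counting period for the 10%, and the documents state neither.

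**What to change.** Reconcile Sections 6.1, 6.2 and 6.3.1 with Table 2 so that each toxicity type has one recovery level and one restart-dose rule. State them in one place and have the other sections refer to it. Replace the backward reference in 6.3.1 with a pointer to that place. Align the cycle-start criterion in 5.1.3 (Required Blood Parameters), or say expressly that it yields to Section 6. In the same amendment, state the period over which the 10% of planned dose is counted, since the effect of hold length on evaluability depends on it.

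Which recovery level and which dose rule are right is the sponsor's clinical decision, and this review proposes neither. The cost is protocol wording and the approval of an amendment under Section 11.5. Sample size and the response criteria do not change.
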